Reduces Ki-67 is considered a good surrogate of response to treatment. Correlating changed in HER protein expression with Ki-67 would be an **innovative approach** to assess the association of HER protein upregulation and tumor responses to endocrine therapy.

[figure not shown]

Figure 3. Tamoxifen-resistant MCW2-I PDX model with upregulated HER2 becomes sensitive to trastuzumab. Note that four of 10 trastuzumab-treated mice did not have tumor 'recurrence' within 90-day treatment period.

Cyclin-CDK-RB Pathway

Another potential pathway of interest in HR+ breast cancers is **the cyclin-CDK-RB pathway** (cyclin dependent kinase-retinoblastoma) that can be altered in luminal breast cancer and appears to be associated with endocrine resistance.²¹ High expression of cyclin-D1 is associated with activation of cyclin-dependent kinases CDK4 and CDK6 and progression to the S-phase of cell cycle. Studies have linked high expression of cyclin-D1 to tamoxifen resistance and high expression of cyclin-E1 to letrozole resistance.^{22,23} **[name] and colleagues at MCW** have extensive laboratory experience with breast cancer xenograft models and have shown that additional mechanisms of resistant ER+ breast cancer may be via the emergence of **basal cytokeratin-5 positive (CK5+)** **progenitor cells**, which display resistance to chemotherapy and tamoxifen.²⁴ **We now want to assess CK5+ progenitor cells in breast cancer tumors and determine if an increased proportion of therapy-resistant CK5+ progenitor cells is negatively correlated with tumor proliferation reduction in response to neoadjuvant endocrine therapy.** Patients with ER+/CK5+ breast cancer may benefit from emerging BCL6-inhibitors and may be harmed by prolactin receptor antagonists.²⁴

Bruton's Tyrosine Kinase (BTK) Expression

Bruton's tyrosine kinase (BTK) belongs to Tec family tyrosine kinases and causes activation of multiple downstream pathways of cell survival and proliferation.²⁵ Recently, an alternate isoform of BTK, BTK-C, was identified as a novel survival factor for breast

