This project is significant and has the potential to have a strong impact because it poses clinically relevant questions. It aims to assess molecular changes with endocrine treatment, facilitating recognition of potential targetable resistance mechanisms and pathways. Our expectations are that the proposed studies will reveal mechanistic and preclinical insight to support novel strategies for improved clinical management of HR+ breast cancer patients. Given the small sample size and the exploratory nature of the study, we may not have enough responses to reach a statistically significant result. However, we expect to determine how frequently the protein levels of HER family of RTKs are increased following endocrine therapy. This information would be useful in selecting patients for a follow-up trial with targeted HER/EGFR therapy. Likewise, we expect to determine the frequency of upregulation in CK5+/ER-negative subpopulation of cancer cells, as well as BTK expression in HR+ breast cancer. This information may be used to select patients to a follow-up trial with BCL6 inhibitor and BTK inhibitor, respectively. Patients with changes in iron-related proteins, such as high ribonucleotide reductase expressions, may benefit from ribonucleotide reductase inhibitors and those with increased PD-1 expression may benefit from PD-1 inhibitors. Lack of a significant radiographic response or change in Ki-67 would potentially be an important prognostic indicator of development of early endocrine resistance.

Taken together, these research aims will characterize the changes in tumor microenvironment and association with tumor responses to endocrine therapy. The knowledge from these studies will help define signaling pathways and

predictive biomarkers of short and long-term responses to endocrine therapy and potential emergence of endocrine resistance in low responding tumors. The results from this project would be critical in providing preliminary data for support for a follow-up phase II randomized study of endocrine therapy, combined with other targeted therapy based on molecular tumor profile.

II. HYPOTHESIS AND OBJECTIVES

Hypothesis

We hypothesize that in HR+ HER2 negative tumors of early stage breast cancer patients, expression of one or more HER proteins (HER1-4) will be upregulated in at least 50% of tumors after four weeks of neoadjuvant endocrine therapy and this upregulation will correlate with Ki-67 expressed in more than 10% of cancer cells.

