The following objectives are designed to test these hypotheses:

Primary Objective

Determine the frequency of increased **HER-protein expression** in tumors following treatment with neoadjuvant endocrine therapy and their association with tumor Ki-67 expression. We will measure cancer cell protein levels of growth factor receptors of the HER family before and after neoadjuvant endocrine therapy. The data will be used to inform a future randomized trial utilizing a combination of endocrine treatment and the most promising anti-HER targeted therapy.

Secondary Objectives and Associative Studies

Our secondary objectives are focused on other biomarkers and pathways of interest. Our goal is to determine changes in gene expression and/or protein levels of the following biomarkers with neoadjuvant endocrine therapy and correlation with tumor responses.

1. Determine whether an increased proportion of **therapy-resistant CK5+ progenitor cells** are negatively correlated with a response in Ki-67 and tumor volume reduction, in response to neoadjuvant endocrine therapy.
2. Assess changes in the **% expression of ER and PR** in pre- and post-treatment breast cancer tumor specimens and their correlations with Ki-67 and radiographic responses.
3. Assess changes in **BTK protein expression** with neoadjuvant endocrine therapy and correlation with responses.
4. Changes in **iron-related protein expression, i.e., transferrin, ferritin, ferroportin and ribonucleotide reductase** with neoadjuvant endocrine therapy and correlation with responses.
5. Changes in PD-L1 and PD-L2 protein expression with neoadjuvant endocrine therapy.

6. Assess changes in tumor size on radiographic images with neoadjuvant endocrine therapy and correlate with changes in biomarkers and Ki-67.
7. Chart review planned at about five years from completion of study to assess patient outcomes, i.e., ipsilateral, contralateral or distant recurrences.

III. ELIGIBILITY CRITERIA

Inclusion Criteria

1. Unilateral diagnostic breast mammogram and ultrasound within 60 days of enrollment.
2. Pathologically proven diagnosis of invasive breast cancer, clinical stage I or II.
3. Patients must be clinically lymph node negative. Lymph node negativity must be confirmed by clinical exam and/or ultrasound imaging.
4. The patient must be female.
5. Age ≥ 18 years.

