3. Purely noninvasive breast cancer (i.e., ductal carcinoma *in situ*, lobular carcinoma *in situ*).
4. Men with breast cancer. Male breast cancer is a rare event and it is unclear if neoadjuvant endocrine treatment approach is safe in men.
5. Medical, psychiatric or other condition that would prevent the patient from receiving the protocol therapy or providing informed consent.
6. Pregnant or lactating women are ineligible.

IV. STUDY DESIGN AND TREATMENT PLAN

General description: This is an exploratory interventional study to investigate changes in HER-protein expression along with other biomarkers of interest and correlations with tumor cell proliferation and responses in patients with HR+ HER2 negative early stage breast cancer treated with neoadjuvant endocrine therapy.

Number of subjects: 37

Primary End point: Determine the frequency of increased protein expression of **HER family of receptor tyrosine kinases** in tumors, following treatment with neoadjuvant endocrine therapy and their correlation with Ki-67 tumor responses.

Secondary End points:

- To determine changes in additional selected molecular markers (CK5+/ER-progenitor cells, PD-L1, PD-L2, BTK, iron-related proteins) and correlate with Ki-

67 responsiveness to endocrine therapy in our pre- and post-treatment tumor specimens.

- Assess changes in tumor size on radiographic images with neoadjuvant endocrine therapy and correlate with changes in biomarkers and Ki-67.

Study Timeline:

Primary completion: We expect that the study will reach primary completion 24 months from the time the study opens to accrual.

Study completion: We expect that the study will reach study completion 36 months from the time the study opens to accrual.

Treatment Plan

1. At MCW, all patients undergo diagnostic mammogram and ultrasound of the breast (standard of care) to further evaluate an abnormal breast finding and to obtain core biopsies for diagnostic purposes. If the tumor is visualized on both imaging modalities, at least the largest bidimensional measurements will be recorded. If possible, three-dimensional measurements of tumors will be obtained.
2. Patients with a diagnosis of ER and/or PR positive, HER2 negative node negative invasive breast cancer would be screened for this study (refer to the schema).
3. Node negativity will be established by clinical exam and/or ultrasound

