9. Core biopsy specimens from the initial biopsy at diagnosis would be used for OncotypeDx assay, as well as for study biomarkers assessments. One hematoxylin and eosin slide and up to 15 to 20 unstained charged slides cut at 4 microns thick would be obtained from pathology blocks with residual tumor. These specimens will be reserved for study labs/biomarkers for pre- treatment after the Oncotype has been completed (if applicable). Biomarkers to be assessed pre- and post-treatment are shown in **Table 1**. Details on handling and preparation of tissue specimen and slides for study evaluations are explained in detail below in section **Pathologic Evaluation and Handling of Tissue Specimens**.
10. If adequate tissue is not available for all study biomarkers to be done, additional biopsies will be requested. However, if the patient declines an additional biopsy and enough tissue is available to obtain some but not all study biomarkers, the patient would still qualify and be enrolled to the study.
11. Patients would undergo unilateral diagnostic mammogram and ultrasound within five days prior to surgery to assess radiographic responses to the pretreatment imaging obtained at diagnosis. The CRC/CRN should notify [name] in Radiology prior to surgery. Diagnostic mammogram and the US are to be assessed using WHO criteria for response.
12. Patients would undergo surgery as planned at the end of the four-week (+/- 1 week) period of neoadjuvant endocrine treatment.
13. Surgical specimen would be use for post-treatment assessments. Changes in proliferation marker Ki-67 between pre- and post-treatment tumor specimens would be assessed by our breast pathologists. One hematoxylin and eosin slide and up to 15 to 20 unstained charged slides cut at 4 microns thick would be obtained from pathology blocks with residual tumor. These specimens will be reserved for study labs/biomarkers for post-treatment. Biomarkers to be assessed pre- and post-treatment are shown in **Table 1**. Details on handling and preparation of tissue specimen and slides for study evaluations are explained in detail below in section **Pathologic Evaluation and Handling of Tissue Specimens**.
14. Any remaining tumor tissue would be banked in MCW Tissue Bank according to the MCW Tissue Bank quality control measures. Specimens would be deidentified. A separate consent form would be used for tissue banking. Patients who do not participate in the Tissue Banking are still eligible.

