15. Patients would be treated per standard-of-care guidelines following surgery. The initial Oncotype Dx assay, if done, would be used by the treating medical oncologist to decide if adjuvant chemotherapy is indicated.
16. A follow-up visit would be scheduled within 30 days from surgery. Further follow-up visits would be per the discretion of the patient's treating physicians, who will follow NCCN guidelines.

17. As standard-of-care treatment, patients will be followed by oncology provider(s) at least annually (+/- 3 months). Cancer outcomes up to five years post-treatment will be collected annually (+/- 3 months) by chart review.
18. Given the short course of study treatment (~3-5 weeks) and none-few low-grade toxicities expected, we expect most of our study patients to complete the 4-week study treatment. Patients should be treated for at least 2 weeks with neoadjuvant endocrine therapy to be considered evaluable for the study end points. All dosed patients with at least 2 weeks of neoadjuvant endocrine therapy received would be included in the analyses.
19. All adverse events grade 3 and above, regardless of attribution, will be collected and reviewed at the required timepoints (screening and/or week 1, and end of treatment visit).

Table 1. Biomarkers to be assess pre- and post-treatment with neoadjuvant endocrine therapy

Biomarkers	End Points
Ki-67	Assess change in proliferation with treatment.
HER tyrosine kinase receptor expression	Assess frequency of increased protein levels of HER1-4 and correlation with response to treatment.
ER% / PR%	Assessment of pre- and post-treatment changes and response to treatment.
CK5+/ER- progenitor cells	Assess proportion of CK5+/ER- cancer cells and correlation with response to treatment.
Iron related proteins	Assess changes in protein expression and correlation with responses.
BTK expression	Assess changes in protein expression and correlation with responses.
PD-L1/PD-L2	Assess changes or emergence of protein expression with treatment and correlation with responses.

Pathologic Evaluation and Handling of Tissue Specimens

1. The surgical specimens will be subject to routine pathological analysis. Routine hematoxylin and eosin (H&E) stain will be used for morphological analysis and for the determination of carcinoma diagnosis. The samples will be assessed by our breast pathologists.

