5. Other less commonly reported side effects are anti-estrogen symptoms, i.e., hot flashes, mood changes and weight changes. Some of the rare but serious side effects, such as ischemic cardiovascular event, thromboembolic event or uterine cancer with tamoxifen are long-term side effects and are not expected to occur during this short course of neoadjuvant treatment. Similarly, decrease in bone density with aromatase inhibitors is a slow and long-term side effect, not expected to be seen during the four-week study period.
6. There are no dose modifications or reductions recommended with endocrine treatment.

VII. STATISTICAL CONSIDERATIONS

Statistical analyses:

Demographic and baseline characteristics, such as age, race, weight, values of all biomarkers pre and post-treatment, response measures will be summarized, using means, standard deviations, medians, ranges for continuous variables, and proportions for categorical variables.

This is an exploratory study to gather information on how frequently protein levels of HER growth factor receptors (HER1-4) are upregulated along with changes in other study biomarkers and correlation with Ki-67 in response to short-term neoadjuvant endocrine in early stage HR+ breast cancer. We hypothesize that expression of one or more HER proteins (HER1-4) will be upregulated in at least 50% of tumors after four weeks of neoadjuvant endocrine therapy and this upregulation will correlate with Ki-67 expressed in more than 10% of cancer cells, as compared to upregulation in 30% or less of tumors without the therapy. The change in Ki-67 expression will be dichotomized, as a categorical variable with $\geq 10\%$ increase coded as high and $< 10\%$ coded as low.

- a) For the primary outcome: An exact binomial one sample test of proportions will be used for to test the hypothesis that proportion of upregulated HER proteins will be at least 50% after therapy versus the null hypothesis that the proportion of upregulated HER proteins is not greater than 30%.
- b) For analyzing - the differences in proportion of upregulated HER proteins between the high difference in Ki-67 and low difference in Ki-67 groups, two sample tests of proportions will be used.

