Early stopping for futility and interim analysis in clinical trials are done to ensure safety of the patients and prevent any unnecessary intervention. This is an exploratory study to understand changes in tumor biology with neoadjuvant endocrine treatment. All study biomarkers including changes in HER family of RTKs are being studied to assess responses and development of endocrine resistance. In this study, patients are being treated with endocrine therapy in the neoadjuvant setting for a short duration of time (4 weeks +/- 1 week) without causing any significant delay in their surgery. They will be treated with the same endocrine therapy in the adjuvant setting for at least 5 years which is standard of care. These drugs are routinely used in neoadjuvant setting in patients deemed to be poor surgical candidates or requiring a delay in surgery for variety of reasons and is considered a safe approach with minimal risk to the patients particularly when used for a short duration as done in this study.

The primary objective of this study is to assess changes/upregulation of one or more HER proteins (HER1-4) after neoadjuvant endocrine treatment. Given the exploratory nature and small sample size of this study, we may not see enough upregulation of HER

proteins to meet statistical significance. Up regulation or lack thereof of HER proteins is not a known prognostic factor for patient outcomes at this time and will not impact the safety or clinical management of these patients. Interim analysis and stopping for futility is not indicated in this setting of an exploratory study where the goal is to understand changes in tumor microenvironment to learn more about tumor responses or lack thereof to endocrine treatment. We expect to get important preliminary data from this exploratory study for future follow up clinical trials.

Missing Data management: Observed data will be included in listings, summary tables and statistical analysis, with counts and proportions of missing data, if any. The only likely source of missing data in our study is the absence of some biomarker information due to lack of tissue specimens. As already mentioned, we will attempt to obtain additional biopsy tissue to complete the information, but in case this is not feasible, the evaluation of these biomarkers will be done dropping the missing samples from the analysis. This missed data is likely to be at random and there will be no imputation of missing data.

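### The hypothesis ties HER upregulation to a Ki-67 level above 10%, but items b) and c) group tumours by a 10% increase in Ki-67, on a scale that is not stated

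*Combined protocol and SAP*

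**What the plan says.** The hypothesis in Section II says that one or more HER proteins will be upregulated in at least half of tumours and that "this upregulation will correlate with Ki-67 expressed in more than 10% of cancer cells". The Protocol Summary (Endpoints and Statistical Methodology) and Section VII repeat this. It describes a level of Ki-67.

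The next sentence of Section VII, also in the summary's Statistical Methodology, changes the variable: "The change in Ki-67 expression will be dichotomized, as a categorical variable with" an increase of 10% or more as high and less than 10% as low. Item b) compares the proportion HER-upregulated between the high- and low-difference groups. Item c) uses the same groups for the other biomarkers.

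Other places differ among themselves:

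- The primary end point in Section IV and the primary objective in the summary concern HER expression "following treatment with neoadjuvant endocrine therapy and their correlation with Ki-67 tumor responses".
- Section II, Primary Objective, has "following treatment with neoadjuvant endocrine therapy and their association with tumor Ki-67 expression", which could be a level.
- Treatment Plan item 13 says "Changes in proliferation marker Ki-67 between pre- and post-treatment tumor specimens would be assessed by our breast pathologists", and Table 1 gives the Ki-67 end point as "Assess change in proliferation with treatment".
- Section VII, Early Stopping for Futility, leaves Ki-67 out: "The primary objective of this study is to assess changes/upregulation of one or more HER proteins (HER1-4) after neoadjuvant endocrine treatment".

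**The concern.** A level after treatment and a change during treatment are different variables, so a test on one is not a test of a hypothesis about the other. The Ki-67 association is part of the primary objective or endpoint in the summary, Section II and Section IV, so this is not a side analysis.

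There are two further difficulties.

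- **Scale.** Ki-67 is itself a percentage of positive cells, so a 10% increase can mean ten percentage points or one tenth of the baseline value. Two analysts following the plan could form different groups, and the choice could be made after the results are seen. Section VII also promises family-wise error control with Bonferroni adjustment, which presupposes a defined test variable.
- **Composition of the low group.** The Background treats a fall as response ("Reduces Ki-67 is considered a good surrogate of response to treatment"), and Future Directions treats absence of change as a possible sign of early resistance. The increase-based split puts both kinds of tumour into the low group.

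**Working it through.** **The plan's own figure.** The only sizing figure is 37, for the one-sided test of 30% against 50% in item a). The arcsine formula gives n = [(1.645 + 0.842) / (2(asin√0.5 − asin√0.3))]² = 36.5, rounded up to 37. (The planned exact test has 74.4% power at 37; that is a separate matter.) Nothing is given for the Ki-67 comparison, so there is no figure to reproduce for items b) and c).

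**The rules side by side.** The pre/post values are examples chosen to show the rules, taking the level as post-treatment.

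| Ki-67 pre → post (%) | Level >10%? | Rise ≥10 points | Rise ≥10% relative |
|---|---|---|---|
| 20 → 20 | yes | low (0) | low (0%) |
| 30 → 15 | yes | low (−15) | low (−50%) |
| 20 → 22 | yes | low (+2) | high (2/20 = 10%) |
| 5 → 9 | no | low (+4) | high (4/5 = 80%) |
| 25 → 36 | yes | high (+11) | high (11/25 = 44%) |
| 15 → 3 | no | low (−12) | low (−80%) |

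In points, a rise of at least 10 from any value above 0% ends above 10%. All disagreement then runs one way: above 10% but coded low. On the relative scale it runs both ways, as 30 → 15 and 5 → 9 show.

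**How often the rules could disagree (assumed inputs).** Lognormal pre/post pairs were simulated, 400,000 per scenario: baseline median 10, 15 or 20% with log-SD 0.7; typical fall 0, 25, 50 or 75%; log-SD of change 0.6 or 1.0; values capped at 95%.

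| | Relative | Points |
|---|---|---|
| Level and change rules disagree, all tumours | 6-45% | 7-55% |
| Coded low, among tumours above 10% | 24-97% | 52-99% |

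**Size of the high group (assumed share p that rise).** With X ~ Binomial(37, p):

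| p | Expected, 37p | P(X ≤ 4) |
|---|---|---|
| 5% | 1.9 | 96% |
| 10% | 3.7 | 69% |
| 20% | 7.4 | 11% |
| 30% | 11.1 | 0.6% |

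Suppose 19 of 37 tumours are HER-upregulated and every tumour in the high group is among them. The two-sided Fisher p is:

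- 4 high: C(19,4)/C(37,4) + C(18,4)/C(37,4) = 3876/66045 + 3060/66045 = 0.105.
- 5 high: 11628/435897 + 8568/435897 = 0.046.

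With four tumours in the high group, even a perfect pattern misses 0.05. The result is sensitive: with 18 HER-upregulated, four high gives 3060/66045 = 0.046.

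**Power of the split against continuous change (assumed normal change, 19 of 37 HER-upregulated, 5-30% in the high group, two-sided 0.05).**

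| Shift in Ki-67 change | Fisher on the split | Wilcoxon on continuous change |
|---|---|---|
| 1 SD | 2-51% | 81% |
| 0.5 SD | 1-15% | 29% |

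Fisher's test is itself an assumption here: item b) names only two-sample tests of proportions and gives no sidedness.

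**The case against.** The best defence is that the analysis variable is clear and only the hypothesis sentence is loose. Section VII says that change is dichotomised, items b) and c) name difference groups, and the end point in Section IV, Treatment Plan item 13 and Table 1 all speak of response or change. The word difference, applied to a marker measured in percent positive cells, also leans towards percentage points. Correcting one repeated sentence would then be enough.

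Much of this is fair. If change was meant, correcting the hypothesis is a legitimate remedy. But the level wording stands in the formal hypothesis and is repeated in the summary and in Section VII. The primary objective in Section II refers to Ki-67 expression, and the Background supports an on-treatment reading as a surrogate for response. The lean towards points is not a statement of scale.

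It can also be said that item a) and the sample size are untouched, that the study is exploratory and warns that significance may not be reached, and that pre- and post-treatment values are collected and summarised, so either variable can be computed later. All of that stands and limits the consequence. It does not remove the room for a choice made after the data are seen. Item d) allows regression of biomarker changes on patient covariates and other predictors, but specifies no model of HER against Ki-67.

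Finally, the simulated ranges rest on inputs that no document supports. They illustrate; the case is made by the wording and the worked examples. The preference for a continuous analysis is a separate improvement, not proof of the mismatch.

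**Conclusion.** The inconsistency is real and should be fixed. The stated hypothesis concerns a Ki-67 level, the planned test concerns an increase, no listed analysis uses the level, and the scale of 10% is undefined. This follows from the text alone. How many tumours would change group cannot be known from the documents; under the assumptions above it ranges from a few percent to about half. Confidence is high that the texts conflict. Which variable was intended remains open. The effect is confined to the association part of the primary endpoint and to the biomarker comparisons in item c).

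**What to change.** Before analysis, settle one Ki-67 variable and use it in the Protocol Summary, Section II and Section VII. State its time point, cut-off and scale, and the sidedness of item b).

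- **If the hypothesis stands as worded:** compare the proportion HER-upregulated between tumours with post-treatment Ki-67 above 10% and those at or below 10%, using Fisher's exact test because groups may be small. State that post-treatment is the time point, since the hypothesis does not say so outright.
- **If change is meant:** reword the hypothesis and say whether 10% is relative or in percentage points. The increase-based split is best kept as descriptive, because it pools falls with no change.
- **In either case:** pre-specify a supporting analysis relating HER status and the other biomarkers to continuous Ki-67 change. This could be a Wilcoxon test, or log post-treatment Ki-67 regressed on log pre-treatment Ki-67 plus HER status, with the offset for 0% values fixed in advance. Report the number of patients with paired Ki-67.

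The cost is minor rewording and a little extra analysis on data already being collected. The level split brings no power gain: for an assumed 70% against 40% HER-upregulated, two-sided Fisher power is 41% at 18 against 19 tumours, 35% at 12 against 25 and 24% at 9 against 28. Treatment Plan item 10 and the missing-data paragraph allow for absent biomarker values. With 33 or 30 pairs (assumed), Wilcoxon power at 1 SD falls from 81% to about 77% or 71%.
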